The spatial maps of ICA- and SCA-derived brain parcels will be compared across groups. First, the participant-specific sensory and motor brain parcels will be converted to z values, so image intensities reflect the degree to which the parcel is present in each participant's data. The brain parcels will be combined in a second-level random effects analysis using a two sample t-test in SPM8. Voxels that contributed unequally to the parcels across groups will be identified using a liberal voxel-wise p value of 0.01 and a cluster-level p value of 0.05 corrected for multiple comparisons². The between network connectivity (BNC) between sensory and motor parcels will be calculated using Pearson's correlation coefficient between pairs of participant specific motor and sensory brain parcels³. Pairwise-correlations will be converted to Z-scores using Fisher's transformation, and the BNC across groups will be compared using two-sample t tests and adjusted p-values using a false discovery rate correction. Next, we will investigate whether sensory and motor BNC measured at week 2 of cycling program are related to motor and sensory International Standards for Neurological Classification of Spinal Cord Injury (ISNCSCI) scores measured at week 4, using a multivariate linear regression model analysis. Finally, the longitudinal inter- and intra-subject reproducibility of the ICA- and SCA-derived brain parcels will be assessed using intra-class correlation coefficient (ICC).

d. Early stopping rules.

[figure not shown]

Figure 2. Correlations between sensorimotor-visual BNC measurements and total ISNCSCI scores in SCI patients suggest a compensatory plastic cortical changes that are related to clinical presentation of the patients. Patients with lower ISNCSCI score showed larger degree of functional connectivity between the sensorimotor and visual networks.

Date: 4.14.2023

Principal Investigator: [name].

Application Number: IRB000182576

The principal investigator may discontinue the study if the interim statistical analysis as described above indicates that the number of subjects required for this trial exceeds 50.

Patients may withdraw from the study at any time for any reason. Any investigator may discontinue a patient for any of the following reasons:

- The subject experiences a medical emergency that necessitates discontinuation of therapy

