development of a robust, clinically feasible rsfMRI data analysis pipeline, this study is expected to result in improved understanding of the functional reorganization that takes place during and after intervention.

4. Study Procedures

- Study design, including the sequence and timing of study procedures (distinguish research procedures from those that are part of routine care).

This will be an early phase 1 (phase 0) clinical trial. Specifically, the study will be performed as a randomized, parallel group trial to determine if the amount of changes in brain functional connectivity outcome measures (i.e., between network connectivity) is significantly different between the group of patients that perform FES cycling and another group of patients that perform passive (sham) cycling.

Patients of the International Center for Spinal Cord Injury (ICSCI) at the Kennedy Krieger Institute (KKI) will be identified as meeting the inclusion criteria by reviewing the medical records held by the ICSCI. Once the patient consents by signing the consent form, official screening of subjects will be performed. Subjects will be randomized into 2 groups: FES cycling (Group 1; n=24) and passive cycling (Group 2; n=24). The patients will undergo either an FES cycling or a passive cycling sessions for 4 weeks, 3 times a week. **Acquisition of rsfMRI measures:** MRI will be performed on all participants at the beginning (prior to cycling sessions) and at the end of the 2nd and 4th weeks of the intervention program. **Acquisition of clinical measures:** ISNCSCI and SCIM (Spinal Cord Independence Measure) evaluations will be performed to coincide with the dates of MRI acquisitions, to determine the neurological level and the degree of sensory and motor impairments. Detailed study timeline can be found in Figure 1.

[figure not shown]

Figure 1. Study Timeline.

- SCI patients assigned to FES cycling group will take part in the following evaluations:
 - Medical chart review / MRI screening questionnaire
 - FES cycling trial
 - Neurological evaluation (ISNCSCI – more commonly known as ASIA exam)
 - Functional evaluation (SCIM)
 - MRI

Date: 4.14.2023

Principal Investigator: [name].

Application Number: IRB000182576

E1: FES cycling

- SCI patients assigned to passive cycling group will take part in the following evaluations:
 - A: Medical chart review / MRI screening questionnaire
 - B2: Passive cycling trial

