Application Number: JRB000182576

included only if one can understand the nature of the experiment as presented in English, and can cooperate with symptom assessment in English. 48 subjects will be recruited in total over a period of two years.

Inclusion criteria:

- Adult (18-99 years) men and women of all ethnic groups
- SCI, traumatic
- Thoracic (T1-T12) and lumbar (L1, L2), without the involvement of lower motor neurons.
- ASIA classification A-D
- Chronic injury: > 6 months from the injury
- Satisfactory general health
- No FES ergometer (i.e. RT300 or equivalent) use within 4 weeks.
- Ability to comply with procedures and follow-up

Exclusion criteria:

- Contra-indication to MR study (*e.g.*, cardiac pacemaker, claustrophobia, aneurysm clip, etc.)
- History or clinical evidence of moderate or severe brain injury
- Major spine deformity (*e.g.* scoliosis, kyphosis, subluxation)
- Movement disorder or severe spasticity preventing ability to lay still for extended periods required for imaging.
- Women who are pregnant
- Concurrent lower motor neuron disease such as peripheral neuropathy that would exclude lower extremity electrical excitability
- Unstable long bone fractures of the lower extremities.
- Subjects with history of inability to tolerate electrical stimulation.

Pregnancy is associated with significant physiological deviations with respect to cerebral spinal fluid dynamics and blood flow in the middle cerebral artery that are different than what is seen in women who are not pregnant. Gonadal steroids associated with pregnancy are also implicated in marked changes in cognitive function. Because of the significant changes from the normal, non-pregnant condition it is important to exclude pregnant women from many studies. If they were not excluded their data would significantly add to the variance of the physiological and behavioral measures. Furthermore, that variance is not readily interpreted at this time.

6. Drugs/ Substances/ Devices

- a. The rationale for choosing the drug and dose or for choosing the device to be used.

The RT-300 FES bike has been FDA-cleared for use in general rehabilitation (the device clearance number is K072398). It has been a standard rehabilitation treatment modality at our center for several years.

- b. Justification and safety information if FDA approved drugs will be administered for non-FDA approved indications or if doses or routes of administration or participant populations are changed.

N/A

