- c. Justification and safety information if non-FDA approved drugs without an IND will be administered.

Date: 4.14.2023

Principal Investigator: [name].

Application Number: IRB000182576

N/A

7. Study Statistics

a. Primary outcome variable.

Type	Name	Time Frame	Brief Description
Primary	International Standard of Neurological Classification for Spinal Cord Injury (ISNCSCI)	baseline, mid-intervention, post-intervention	Developed by the American Spinal Injury Association (ASIA) as a universal classification tool for spinal cord injury (SCI). The classification tool involves a sensory and motor examination to determine the neurological level of the injury and whether the injury is complete or incomplete. The tool also provides sensory and motor scores of upper and lower body, as well as right and left of the body. The ISNCSCI defines neurological level as the most caudal level at which sensory and motor function are intact. The completeness of the injury is graded according to the ASIA Impairment Scale (ISNCSCI).
Primary	Resting state fMRI functional connectivity	Baseline, mid-intervention, post-intervention	RsfMRI functional connectivity is defined as the temporal dependency of neuronal activation patterns (represented by the blood oxygenation level dependent (BOLD) signal time courses as measured using rsfMRI) of anatomically separated brain regions. There are number of methodologies one can use to characterize the degree and type of rsfMRI functional connectivity. One example is between-network-connectivity (BNC), which is defined as the degree of correlation between two time courses obtained from a pair of brain regions. Summary statistics of BNC (e.g., mean, variance), as well as the dynamic properties of BNC (e.g., dynamic functional connectivity) can be used to further summarize the characteristics of the functional connectivity in SCI population.
Primary	RsfMRI brain parcels	Baseline, mid-intervention, post-intervention	RsfMRI functional connectivity can also be used to identify functionally homogeneous brain regions, or parcels of the brain. The parcels' center of mass, spatial maps, average and variance of the BOLD signal time courses within the parcels can be used to characterize brain functional organization.

b. Secondary outcome variables.

Type	Name	Time Frame	Brief Description

Date: 4.14.2023

Principal Investigator: [name].

Application Number: IRB000182576

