Secondary	FES cycling parameters	During intervention	The degree of electrical stimulation is adjusted specifically for each patients, depending on the patients level of sensory and motor impairment, as well as the patient's level of tolerance for sensation and fatigue. Accordingly, the strength and frequency of the electrical stimulation applied during each FES cycling session will be recorded. The duration of the cycling session performed will also be recorded. These parameters may be used as higher-order confounds during statistical data analysis
Secondary	Passive cycling parameters	During intervention	The amount of time and the degree of resistance used by the patients during the passive cycling sessions will be recorded, and may be used as higher-order confounds during statistical data analysis.
Secondary	Personal information	Baseline	Patient's age, sex, handedness, and time since injury will be recorded, and may be used as higher-order confounds during statistical data analysis.
Secondary	SCIM	baseline, mid-intervention, post-intervention	The Spinal Cord Independence Measure Version III (SCIM-III) assesses daily living and mobility activity performances. Specifically, it assesses the degree of self-care (feeding, grooming, bathing, and dressing), respiration and sphincter management, and mobility abilities (bed and transfers and indoors/outdoors) and each category are scored using the SCIM questionnaire. SCIM-III is frequently used in both clinical practice and clinical trial settings and is used to help guide clinicians in determining treatment goals and objectives for patients with an SCI.

c. Statistical plan including sample size justification and interim data analysis.

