Preliminary study: In this preliminary study, we hypothesized that BNC of sensorimotor and visual networks will correlate with the total ISNCSCI score, and performed the study to determine the feasibility of a larger population study. Twelve SCI patients were recruited, and the relationship between the ISNCSCI score and BNC measurements was examined. ISNCSCI sub-scores were first obtained, which were: total upper and lower body motor scores, and total sensory score. The sum of the three scores provided the total ISNCSCI scores. Analysis of the data consisted of preprocessing, PCA, and GICA, and total of 14 intrinsic functional components were identified. BNC between the sensorimotor and visual networks were computed, and plotted against the total ISNCSCI scores. Linear regression analysis was performed to find the best linear fit for the plots. Stronger BNC between the sensorimotor and visual networks was associated with lower total ISNCSCI scores ($R^2=0.35$, $p = 0.04$; [Figure 2](#)[Figure 2](#)). In other words, patients with greater degree of physical impairment tended to have stronger functional connectivity between the sensorimotor and visual networks, suggesting compensatory plastic cortical changes that are related to clinical presentation of the patients. Overall, BNC measures showed good correlations with the total ISNCSCI scores, supporting our hypothesis.

Between network connectivity (BNC) measurements from the above preliminary study provided means, standard deviations, and correlation coefficients for 12 SCI patients. A power analysis¹ revealed that a sample size of 24 subjects will be required to achieve 80% power at an alpha of 0.018; the alpha level was lowered with the correction for multiple comparisons in mind. We will therefore recruit a total of 48 patients. At this point, we do not have enough information about the variability of the BNC in response to the FES to perform a more stringent power analysis. We will use the data in the first 24 SCI subjects recruited to the study to assess the degree of variability in the metric. Based upon these estimates, we will then perform a power analysis to determine how many more subjects will need to be enrolled to assess the significance of our findings.

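### Patients with AIS grades A to D are all admitted, but neither the between-arm BNC test nor the Aim 2 regression adjusts for baseline severity, which is already measured at week 0

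*Combined protocol and SAP*

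**What the plan says.** - **Entry (section 5).** The criterion is "ASIA classification A-D", so complete and incomplete injuries are both eligible. No quota or cap by grade is given.
- **Allocation (section 4a).** "Subjects will be randomized into 2 groups: FES cycling (Group 1; n=24) and passive cycling (Group 2; n=24"). No randomisation method or stratification factor is given anywhere.
- **Patient covariates (section 7b).** "Patient's age, sex, handedness, and time since injury will be recorded, and may be used as higher-order confounds during statistical data analysis". AIS grade, neurological level and baseline ISNCSCI are not listed, and use of the listed items is optional.
- **Severity is measured (section 7a).** ISNCSCI is taken at baseline, and "The completeness of the injury is graded according to the ASIA Impairment Scale (ISNCSCI").
- **Arm comparison (section 7c).** "the BNC across groups will be compared using two-sample t tests", with a false discovery rate correction and no covariate.
- **Aim 2.** Section 2 correlates the week-2 change in BNC with the week-4 change in ISNCSCI. Section 7c instead relates BNC measured at week 2 to ISNCSCI measured at week 4, in a regression with no named covariates.
- **Why severity might matter.** Section 3 (Resting State Functional MRI) ties structural integrity at the injury site to the capacity for recovery. The pilot in section 7c reports that "patients with greater degree of physical impairment tended to have stronger functional connectivity between the sensorimotor and visual networks" (R² = 0.35, p = 0.04; "Twelve SCI patients were recruited").

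**The concern.** The trial wants to show that an early BNC signal predicts later neurological improvement. AIS grade is known before the first cycling session. If BNC and ISNCSCI both follow severity, they will correlate across a group of mixed grades even when BNC adds nothing to the grade, and the planned Aim 2 analysis could not tell this from genuine prediction. A marker that only restates the entry examination would not support early adjustment or termination of an intervention, which is the use the abstract proposes.

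The between-arm BNC comparison raises a separate and smaller matter. A chance imbalance in completeness between two arms of 24 would go uncorrected in an unadjusted t test.

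**Working it through.** **1. The plan's sample size.** Section 7c states that "a sample size of 24 subjects will be required to achieve 80% power at an alpha of 0.018" but does not name the effect size. Assume it is the pilot correlation, r = √0.35 = 0.592.
- Pilot p-value: t = 0.592 × √10 / √0.65 = 2.32 on 10 df, p = 0.043. This matches the stated 0.04.
- Fisher z, n = ((z_α + z_β) / atanh r)² + 3. Two-sided: ((2.366 + 0.842) / 0.680)² + 3 = 25.2, so 26. One-sided: ((2.097 + 0.842) / 0.680)² + 3 = 21.7, so 22.
- Simulated two-sided power at n = 24 is 78.9%.

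The stated 24 is therefore consistent with a single-group correlation test at alpha 0.018. That alpha and n = 24 (the FES arm) are used below for Aim 2. The two-sided critical |r| is 0.479.

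**2. Aim 2 as section 7c words it (week-2 BNC against week-4 ISNCSCI).** Suppose the two are linked only through baseline severity. Then |r| = |r(severity, BNC)| × r(baseline ISNCSCI, week-4 ISNCSCI). The first factor is the pilot 0.592. The second is not in the documents; assume 0.80 to 0.95.

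| Assumed baseline-to-week-4 r | Induced \|r\| | Significant at 0.018, n = 24 (simulated) |
|---|---|---|
| 0.80 | 0.592 × 0.80 = 0.47 | 51% |
| 0.90 | 0.592 × 0.90 = 0.53 | 65% |
| 0.95 | 0.592 × 0.95 = 0.56 | 72% |

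The Fisher approximation gives 50%, 64% and 71%.

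**3. Aim 2 as section 2 words it (change against change).** Assume a share p = 0.5 of complete injuries, a mean difference of d SD between complete and incomplete patients on both changes, and no association within either group. Then r = p(1−p)d² / (1 + p(1−p)d²).

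| d on both changes | Induced r | Unadjusted false positives at 0.018 | With completeness in the model |
|---|---|---|---|
| 0.5 | 0.0625 / 1.0625 = 0.06 | about 2% | about 1.8% |
| 1.0 | 0.25 / 1.25 = 0.20 | about 8% | about 1.8% |
| 1.5 | 0.5625 / 1.5625 = 0.36 | about 27% | about 1.8% |
| 2.0 | 1 / 2 = 0.50 | about 63% | about 1.8% |

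These rates take exactly 12 of 24 patients as complete. If the number varies by chance around half, they are about 2%, 7%, 26% and 59%. If completeness affects only one of the two changes, induced r is 0 and the rate stays nominal. For the induced r to reach the critical 0.479, 0.25d² = 0.479 / 0.521 = 0.919, so d is about 1.9 on both changes.

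**4. Arm comparison.** Under simple allocation of 48 patients to 24 and 24, with 24 complete (assumption), the hypergeometric probability of a gap of 6 or more complete patients (25 points) is 0.148; with 16 complete it is 0.125. Given a 25-point gap, the shift in BNC change is 0.25d / √(1 + 0.25d²), or 0.12, 0.22 and 0.30 SD for d = 0.5, 1 and 1.5. The type I error conditional on that gap, at nominal 5%, is about 7%, 12% and 17%. Averaged over all allocations it remains nominal.

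**The case against.** The strongest reply is that the documents never show severity driving change. The pilot is cross-sectional, has 12 patients, and relates the level of sensorimotor-visual BNC to total ISNCSCI. It examined neither AIS grade, nor change, nor the sensory-motor BNC planned here. Section 3 is qualitative and concerns structural integrity. This stands: a reader might infer that completeness is a main determinant of change in both measures, and the documents do not support that. Differencing would also remove much of a link between levels, and with differences of 0.5 SD or less the change-on-change analysis is hardly affected.

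Three further inferences are tempting and should not be drawn.
- *That randomisation is unstratified.* Section 4a gives group sizes and is silent on method.
- *That missing stratification produces the Aim 2 correlation.* Aim 2 concerns patients in the FES programme. Any confounding there comes from mixed severity within the arm, and stratified allocation would not remove it.
- *That the arm comparison is biased, or that imbalance at the 24-patient interim misleads.* Randomisation keeps the t test valid on average. Sections 7c and 7d use the interim to assess BNC variability and recalculate sample size, and describe no interim test between arms.

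Section 7b also records FES stimulation strength, set partly by impairment, as a possible confound. That is a partial proxy for severity, but it is optional, also depends on tolerance and fatigue, and is measured during treatment. It does not replace a baseline value.

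**Conclusion.** The point holds as an omitted baseline covariate. The plan admits all grades, measures severity at week 0, gives its own grounds for thinking severity relates to BNC and to recovery, and then leaves it out of both analyses.

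Exposure is greatest under the section 7c wording of Aim 2. The 51-72% there rests on the pilot correlation carrying over to the networks and sub-scores analysed, and on the assumed ISNCSCI stability of 0.80-0.95. Under the section 2 wording the harm runs from negligible to large according to assumed differences that the documents cannot settle, and it requires an effect on both changes. For the arm comparison the issue is chance imbalance and precision, not bias.

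This is worth correcting because the remedy is nearly free and the biomarker claim depends on it. It does not show that a positive Aim 2 result would be spurious.

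**What to change.** 1. In section 7b, add week-0 AIS grade (A versus B-D) or baseline ISNCSCI score to the patient covariates, and make its use mandatory.
2. In section 7c, replace the unadjusted two-sample t tests with a linear model of BNC change on arm plus that covariate, keeping the false discovery rate correction.
3. Run the Aim 2 regression on change scores, as section 2 has it, with the covariate as a fixed term, and reconcile the section 7c wording. If week-2 and week-4 values were kept instead, the covariate should be the baseline ISNCSCI score, because a two-level grade captures severity only in part.
4. Base the claim of prediction on the adjusted BNC coefficient. Do not require separate tests within grade: with about 12 patients per stratum, power at the pilot r and alpha 0.018 falls below 40%, against 79% at n = 24.
5. State the randomisation method. Stratifying remaining allocations by A versus B-D is an optional precision aid for the arm comparison and does nothing for Aim 2.

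The cost is one model degree of freedom, with no added visits, measurements or patients. If BNC change does track severity, the adjusted coefficient will also be less precise. At a squared correlation as high as the pilot's 0.35, its variance rises by 1 / (1 − 0.35) = 1.54, which reflects how little BNC would then add to the grade.

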 - C1: Neurological evaluation (ISNCSCI – more commonly known as ASIA exam)
 - C2: Functional evaluation (SCIM)
 - D: MRI
 - E2: passive cycling

A: Medical chart review / MRI screening questionnaire

For all subjects with spinal cord injury, their medical chart will be reviewed for the following information:

Demographics

Medical history (including labs)

Physical history

Neurological history

Medication history

Therapeutic plan

Physical/occupational/aquatic therapy history (including outcome measures)

This information is obtained as part of a routine care. The participant does not have to be physically present during this process. At this time, a standard MRI screening questionnaire will also be completed to be sure that it is safe for the participant to have an MRI exam.

B: Cycling trial

B1. FES cycling trial: This is a routine exam performed for people with spinal cord injury at the ICSCI.

Once medically cleared to start an exercise program, subjects who are assigned to the FES cycling group will undergo a trial use of the FES cycle. This trial of FES will be overseen by a trained physical therapist experienced at setting up the FES cycle. The goal of this will be to ensure that the patient is willing and able to use the cycle. Participants who fail the FES trial will be excluded from the study. For additional details regarding the FES component, please see the **E: Cycling** section below. If the patient has successfully participated in an FES cycling program previously, this step will be omitted.

B2. Passive cycling trial: This is a routine exam performed for people with spinal cord injury at the ICSCI.

Once medically cleared to start an exercise program, subjects who are assigned to the passive cycling group will undergo a trial use of the FES cycle (**but with the stimulation component OFF**). This trial of passive cycling will be overseen by a trained physical therapist experienced at setting up the FES cycle. The goal of this will be to ensure that the patient is willing and able to use the cycle. Participants who fail the passive cycling trial will be excluded from the study. For additional details, please see the **E: Cycling** section below. If the patient has successfully participated in an FES cycling program previously (with or without the stimulation component), this step will be omitted.

C: Neurological evaluation

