E1. Functional Electrical Stimulation cycling: The FES cycling group (Group 1) will use RT300 ergometer (Restorative Therapies, Inc., Baltimore, Maryland). The RT300 ergometers are currently installed at ICSCI according to Kennedy Krieger Institute and Johns Hopkins Hospital safety guidelines. The muscles chosen for stimulation will be the bilateral glutei, quadriceps and hamstrings. The FES stimulation parameters will be set as follows: waveform biphasic, charged balanced; phase duration typically of 250 microseconds; pulse rate 33 to 45 pulses per sec (pps). The stimulus intensity of each channel will be adjusted for individual patients and muscle group so that a tolerable stimulation is provided that will generate a cycling action (0-140 mA). Target cycling speed is 50 RPM. Resistance will be automatically adjusted by the FES bike according to the subject's performance. When fatigue occurs, participants will continue cycling with electrical stimulation and motor support. FES therapy will be administered for one hour per session 3 times a week.

E2. Passive cycling: The passive cycling group (Group 2) will use the same RTI 300 ergometer however during this period stimulation will not be turned on. Instead, continuous motor support will be activated resulting in passive cycling. Target cycling speed is 50 RPM. Participants assigned to passive cycling will be required to have one hour of passive therapy 3 times a week for the entire duration of treatment assignment.

b. Study duration and number of study visits required of research participants.

Patients will be evaluated for appropriateness of enrollment and informed consent will be obtained. During the next 8 weeks, the screening process will be completed. A trial of FES will be performed at Kennedy Krieger Institute ICSCI to ensure that the participant is able to tolerate the stimulations of this exercise modality. If he or she is willing and able to proceed with the study then baseline data will be obtained at the beginning of week 1. The detailed study timeline can be found in Figure 1. The study duration for each assessment is as follows:

A: Medical chart review: N/A

B: FES/passive cycling trial (30 min)

C1: Neurological evaluation (up to 1 hour, part of routine care in ICSCI; total of 3 times over 4 weeks)

C2: Functional evaluation (up to 45 min, part of routine care in ICSCI; total of 3 times over 4 weeks; to be performed simultaneously during one of E1 or E2 sessions)

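### As B1 and B2 are written, stimulation intolerance first found at the cycling trial excludes patients from the FES arm only; Section 4b reads differently, and the two must be reconciled

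*Combined protocol and SAP*

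**What the plan says.** Section 4 (study design) describes a randomised parallel-group trial, 24 patients per arm, to "determine if the amount of changes in brain functional connectivity outcome measures" differs between FES and passive cycling. Section 4e relies on the same contrast to attribute connectivity changes to FES, and Section 7c tests BNC between groups with two-sample t tests and a false discovery rate correction.

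The cycling trial is described in three places.

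- **B1 and B2.** In B1, "subjects who are assigned to the FES cycling group will undergo a trial use of the FES cycle", and "Participants who fail the FES trial will be excluded from the study". In B2, passive-assigned patients try the same cycle, "but with the stimulation component OFF", and failures are also excluded. B1 waives the trial after an earlier successful FES cycling programme. B2 has the same waiver but counts programmes with or without stimulation.
- **Evaluation lists in Section 4.** These are set out by arm ("SCI patients assigned to FES cycling group will take part in the following evaluations"), and each includes its own arm's trial. The text just before them puts screening after consent and ahead of the randomisation sentence: "Once the patient consents by signing the consent form, official screening of subjects will be performed".
- **Section 4b.** After a sentence allowing 8 weeks for screening it says: "A trial of FES will be performed at Kennedy Krieger Institute ICSCI to ensure that the participant is able to tolerate the stimulations". If the participant is willing and able to proceed, "then baseline data will be obtained at the beginning of week 1". No arm is named. The duration list in the same section, however, gives a single 30-minute item covering an FES or passive trial.

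Section 5 excludes a history of intolerance to electrical stimulation in both arms. Section 7c gives no rule for analysing or reporting patients excluded after assignment.

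**The concern.** Randomisation makes the arms comparable only if later exclusions do not depend on the arm. Under B1 and B2, two patients with the same undiscovered intolerance are treated differently: the one assigned to FES leaves the study and the one assigned to passive cycling stays. The FES arm is then a tolerance-selected subset, while the passive arm is not.

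This matters if tolerance is related to change in BNC. A link is plausible from the document itself. Section 4c says that many participants will have residual motor and sensory function and will feel which intervention they receive. Section 7b says that stimulation is adjusted to each patient's impairment and tolerance. If, for example, patients with more preserved sensation fail more often, the FES arm loses them selectively, and part of any between-arm difference could reflect selection rather than stimulation. The direction is unknown.

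**Working it through.** **1. The passages side by side.**

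| Place | When is the trial? | Who is stimulated? | Who is excluded for intolerance found there? |
|---|---|---|---|
| B1 and B2 | After assignment | FES arm only | FES arm only |
| Evaluation lists, Section 4 | Listed by assigned arm | Not stated beyond the trial's name | Not stated |
| Section 4b narrative | Beside screening, before baseline | No arm named | No arm named |
| Section 4b duration list | Not stated | FES or passive trial | Not stated |

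B1 and B2 are the only places that state the rule in full, and they make it depend on arm. The Section 4b narrative fits a single trial for everyone, but its own list does not clearly support that. Placing the trial before baseline does not settle the matter, because assignment can also precede baseline.

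**2. Who is affected.** Only patients with no earlier successful FES cycling (others are waived), no known history of intolerance (already excluded by Section 5), and a failed trial although E1 adjusts intensity to a tolerable level.

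**3. Size, under assumptions.** The plan gives no failure rate and no tolerance-outcome relation, so it has no figure of its own to reproduce. From the plan: 24 per arm (Section 4) and alpha 0.018 (sample-size statement, Section 7c). Assumed: f, the share of FES-assigned patients failing, and d, the difference in BNC change between tolerant and intolerant patients in SD units.

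The passive mean is (1 − f) × tolerant mean + f × intolerant mean. The FES arm under no treatment effect has the tolerant mean. The difference is f × d. With 24(1 − f) left in the FES arm, SE = √(1/24 + 1/(24(1 − f))).

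| f | Expected exclusions, 24f | P(at least one), 1 − (1 − f)^24 | SE | Bias at d = 0.5 | Bias at d = 1.0 |
|---|---|---|---|---|---|
| 5% | 1.2 | 71% | 0.292 | 0.025 SD (0.09 SE) | 0.05 SD (0.17 SE) |
| 10% | 2.4 | 92% | 0.297 | 0.05 SD (0.17 SE) | 0.10 SD (0.34 SE) |
| 20% | 4.8 | 99.5% | 0.306 | 0.10 SD (0.33 SE) | 0.20 SD (0.65 SE) |

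For scale, the difference detectable with 80% power at two-sided 0.018 and 24 per arm is (2.366 + 0.842) × √(2/24) = 0.93 SD. A bias of 0.05 SD is about 5% of that.

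The error rate of one uncorrected two-sided test is Φ(−2.366 + b) + Φ(−2.366 − b), with b the bias in SE. At d = 0.5 it is 0.0184, 0.0196 and 0.0243 for f = 5%, 10% and 20%. In the extreme corner (f = 20%, d = 1.0) it is 0.045.

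**4. A second model.** Suppose tolerance acts only through a baseline clinical score. Borrow r = √0.35 = 0.592 from the 12-patient pilot in Section 7c. Change then correlates with that score at r√((1 − ρ)/2), where ρ is the assumed baseline-to-follow-up correlation; at ρ = 0.7 this is 0.229. Truncating the score at the failure fraction shifts its mean by 0.109, 0.195 and 0.350 SD for f = 5%, 10% and 20%, so the change shifts by 0.025, 0.045 and 0.080 SD. The error rate is 0.0184, 0.0193 and 0.0220. Varying ρ from 0.5 to 0.9, and letting tolerance correlate only 0.5 with the score, gives an overall range of 0.018 to 0.025.

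Both models give zero bias if tolerance is unrelated to the change, or if exclusion does not depend on arm.

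**The case against.** The strongest reply is that Figure 1, to which Sections 4 and 4b both refer for the timeline, may place the trial before randomisation for everyone. Section 4 also mentions screening before randomisation. If so, only wording is at fault. This stands as a limit: one-arm exclusion is what B1 and B2 say, but not the only possible reading of the document. It does not remove the need to reconcile the text.

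Second, the affected group is narrow and both arms exclude trial failures. That is true and is why the bias is probably small. But Section 5 covers only a known history, the waiver covers only earlier successful users, and a stimulation-free trial cannot detect intolerance of stimulation.

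Third, the error rates rest on assumptions. This also stands. The alpha of 0.018 comes from the sample-size statement, whereas the planned BNC tests use false-discovery-rate-adjusted p-values. The pilot correlation is cross-sectional and concerns sensorimotor-visual BNC and total ISNCSCI score, not the sensory-motor BNC compared here. The figures show scale and do not estimate the trial's error rate.

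A reader might infer that the whole trial is compromised or that the sample size falls short. The documents support neither. Aims 1 and 2 are stated within arm and do not rest on comparability between arms, and Section 7c plans to reassess the sample size after the first 24 patients.

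**Conclusion.** The concern holds as a textual conflict with a possible, probably small, selection bias. As B1 and B2 stand, the exclusion rule depends on the assigned arm and operates after assignment; Section 4b can be read otherwise. The comparison exposed is the between-arm BNC comparison in Sections 4, 4e and 7c.

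The size cannot be computed from the documents. With assumed failure of 10% or less and a tolerant-intolerant difference of 0.5 SD or less, the bias is at most 0.05 SD. It becomes material only near 20% failure with a 1 SD difference. A reader might infer a proven or large inflation of false positives; the documents give no failure rate and no tolerance-outcome relation on which to base that. Severity is minor to moderate: the reason to act is that the rule is contradictory and cheap to repair.

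**What to change.** Reconcile the study-design text and evaluation lists in Section 4, B1 and B2, Section 4b and Figure 1, so that exclusion for trial failure does not depend on assigned arm. Two routes do this:

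1. Complete the trial, with one pass rule and one waiver rule, in screening before randomisation for everyone, as the Section 4b narrative suggests.
2. Keep patients who fail after assignment in their assigned arm, with MRI and ISNCSCI measured and analysed.

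The investigators decide which, including who receives stimulation. Either way, state in Section 7c that the between-arm BNC comparison is by assigned arm, and report post-assignment exclusions by arm. If Figure 1 already places one common trial before randomisation, the change to the trial description is only one of wording.

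The cost is a protocol amendment. The trial is a 30-minute routine exam already planned in both arms, and 8 weeks are allowed for screening. Route 1 may bring a brief stimulation exposure before baseline for future passive-arm patients, which must be squared with the criterion of no FES ergometer use within 4 weeks. It also needs a few more patients screened: 48/(1 − f) is at most about 51, 54 or 60 at assumed failure of 5%, 10% or 20%, fewer with waivers. Route 2 needs outcome visits for patients who do not take up the assigned cycling. If enrolment is under way, some patients will have entered under each rule, and the report should say so.
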